Analysis approach

Statistical analysis will be performed by Stata, version 15. The baseline characteristics will be assessed by arm. The primary analysis will be an intention-to-treat (ITT) analysis. We will compare the mean length velocity (cm/ month) (primary outcome), weight velocity (gm/kg/day), LAZ, WLZ, and WAZ between the two intervention arms and the control arm using ANOVA, with the model adjusted for the birth weight and age of the infants at enrollment. If an outcome is missing for the intention-to-treat infants, the means from that group will be imputed.

Safety outcomes

i. Maternal serious adverse events

The occurrence of maternal SAEs will be expressed as the proportion of women with at least one SAE during the follow-up period (from enrolment to 179th day). The proportion will be calculated by dividing the number of women with at least one recorded SAE by the total number of enrolled participants. Results will be shown both as proportions of participants with any SAE as well as tabulated by the SAE category (death, hospitalization, other). If any participant has experienced more than one type of SAE, the participant will be recorded in each category.

ii. Infant serious adverse events

The occurrence of infant SAEs will be expressed as the proportion of babies with at least one SAE during the follow-up period (from enrolment to 179th day). The proportion will be

calculated by dividing the number of babies with at least one recorded SAE by the total number of recorded newborns. Results will be shown both as proportions of participants with any SAE as well as tabulated by the SAE category (death, hospitalization, other). If any participant has experienced more than one type of SAE, the participant will be recorded in each category.

Interim analysis

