The null hypothesis for this trial is that the mean difference in length velocity between an infant of a lactating woman receiving standard breastfeeding counseling with BEP alone (Intervention arm 1) for 6 months or in combination with a single prophylactic dose of azithromycin at 42 days of age (Intervention arm 2) and an infant of a lactating woman receiving standard breastfeeding counseling alone (control arm) is equal or less than 0.12 cm/month (primary outcome). Due to the absence of evidence of such interventions on length velocity, we based this hypothesis on our local experience and field data from our field sites. The alternate hypothesis for this trial is that an infant of a lactating woman receiving BEP alone for 6 months or in combination with a single prophylactic dose of azithromycin at 42 days of age has a mean length velocity is greater than 0.12 cm/month that of an infant of a lactating woman not receiving an intervention at 6 months. The sample size takes multiple comparisons into account and is based on the primary outcome of length velocity with an effect size of difference of 0.12 cm per month between the arms (i.e., 0.72 cm difference at 6 months), a 1-sided test, power of 80% and an alpha of 0.025 to account for multiple comparisons (the lower alpha – Bonferroni correction was used). A drop-out rate of 14% (i.e., 10% loss to follow up and infant mortality rate of 4%) is assumed in the study, so the minimum total sample size required is 957 (319 lactating women in each arm).

7. Eligibility criteria

Inclusion Criteria

- a) Lactating women with a mid-upper-arm-circumference (MUAC) of < 23.0 cm
- b) Infants with a live birth outcome, captured within 168 hours (0-6 days)
- c) Individuals with the intention to stay in the catchment area for entire duration of trial after enrollment
- d) Individuals with the intention to exclusively breastfeed child for at least 6 months of age
- e) Individuals who have provided voluntary written informed consent

Exclusion Criteria

- a) Newborns with a birth weight of less than 1500 grams
- b) Newborns with a known congenital anomaly or other severe illness based on the study physician's assessment before enrollment.
- c) Lactating women with known allergies to peanut, lentils, chickpea or dairy products
- d) Individuals who were previously enrolled in the trial

8. Blinding

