10.4. Outcome related to serious adverse events

Adverse and serious adverse event reporting and categorization

- Vomiting: Persistent vomiting or projectile vomiting in an infant reported by mother, within duration of 6 months (Observed or reported).
- Poor feeding/suck: If an infant develops poor feeding/suck or is unable to feed within duration of 6 months (Observed or reported).
- Necrotizing Enterocolitis: Abdominal distention/tenderness, bowel movements, signs of infection such as apnea (stop breathing), and lethargy within duration of 6 months (Observed or reported).
- Diarrhea: Loose stool in an infant reported by mother, lead to severe dehydration, within duration of 6 months (Observed or reported).
- Respiratory: Respiratory distress: Fast breathing (60 or more breathes per minutes) and/or severe chest in drawing and/or baby turn bluish, within duration of 6 months (Observed or reported).
- Rash: An appearance of itchy, red, painful, and irritated skin, visible by health worker or reported by family, within duration of 6 months (Observed or reported).

Serious Adverse Event

Any adverse event will be labeled as a “Serious Adverse Event” (SAE) if it leads to:

- Intravenous therapy
- Hospitalization
- Life threatening situation
- Death

This is defined per clinician’s assessment

Definition of mortality

Infant Mortality	Any infant death under one year of age. ⁴ An agreement was reached to also capture cause of death ⁵ , date of death, and time of death (if death is within 7 days of birth).
Neonatal mortality	Deaths among live births during the first 28 completed days of life (0-27 days). Rate (per 1000 live births) Numerator: # deaths <28 days Denominator: # live births
Maternal Mortality	Maternal death from any cause related to or aggravated by pregnancy or its management (excluding accidental or incidental causes), during pregnancy and childbirth, or within 42 days of termination of pregnancy.

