The primary analysis will be by intention-to-treat (ITT) perform for those who had anthropometry at 6 months. All analyses will be done using Stata software version 16. The WHO 2009 Child Growth Standards will be used for age-sex standardization of child length, weight, head circumferences, MUAC and weight-for-height. Descriptive analysis of each arm will be conducted, and percentages or continuous data with SD will be reported.

The baseline characteristics will be assessed by arm. Outcomes of mean length velocity, growth velocity, weight gain, z scores and change in z score from 0-6 month will be compared using one way analysis of variance (ANOVA). Tukey's test will be used for multiple comparisons. As determined *a priori* the analysis will be adjusted for the birth weight and length of infant, maternal MUAC at enrollment, maternal age, gravida, maternal body mass index and gender of child using general linear model (GLM). Mixed model analysis will be used to compare change in outcome per month in the intervention arm compared to the control arm. Using repeated measures ANOVA, the analysis will report beta coefficients and 95% CI. The coefficients represents the rate of change in outcome per month. For covariate adjustment, an unadjusted and stepwise adjusted model will be run. Trajectories will be plotted for mean length and weight by age for each arm, and monthly z scores were also be plotted.

13. Potential sub-group analysis

The following variables will be considered for sub-group analysis for primary and secondary outcomes:

1. Birth weight i.e. <2500 gm and => 2500 gm
2. Maternal MUAC at enrolment i.e. < 21.0 cm and =>21.0 cm
3. Maternal age i.e. <30 years and => 30 years
4. Gravidity i.e. <3 and =>3
5. Maternal BMI i.e. <18.5 kg/m² and =>18.5 kg/m²
6. Gender of child

14. Missing Data

We will treat missing data as it is, no imputation will be applied. We discussed that due to growth flattering during this age, imputation maybe unreliable.

15. Interim analysis

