¶ Wasting was defined as a weight-for-height z score lower than -2 SD.

[figure not shown]
|| Underweight was defined as a weight-for-age z score lower than -2 SD.

Table 3 | Outcomes at 6 months in the Intention-to-treat analysis*

[figure not shown]
Outcomes	Standard of care and only exclusive breastfeeding counselling	BEP with standard of care and exclusive breastfeeding counselling	BEP plus single dose of azithromycin to infant with standard of care and exclusive breastfeeding	Pairwise comparison $\Delta \pm SD$	p-value
	N=	N=	N=		
Primary outcomes - Mean					
Length velocity of infant (cm/mon)					
Secondary outcomes					
Infant related					
Growth – Mean					
Growth velocity (gm/kg/day)					
Mid-upper-arm-circumference (cm)					
Head circumference (cm)					
Length-for-age z-score					
Weight-for-age z-score					
Weight-for-length z-score					
Head circumference-for-age z-score					
Nutritional status - no./total no. (%)					
Wasting					
Stunting					
Underweight					
Adverse event - no./total no. (%)					
Infant deaths					
Hospitalization					
Injectable therapy					
Maternal related					
Nutritional status - Mean					
Maternal weight gain (kg)					
Mid-upper-arm-circumference (cm)					
Body mass index (kg/m ²)					
Adverse event - no./total no. (%)					
Infant deaths					
Hospitalization					
Injectable therapy					

* Plus–minus values are means \pm SD.

Figure 2 | Monthly trends for z-scores
2a | Monthly mean length-for-age z-scores

2b | Monthly mean weight-for-age z-scores

2c | Monthly mean weight-for-length z-scores

[figure not shown]

Table 4 | Subgroup analysis

Indicator	1	2	3	Δ	P-value	1	2	3	Δ	P-value	1	2	3	Δ	P-value	1	2	3	Δ	P-value	1	2	3	Δ	P-value					
Subgroups	Mean length velocity (cm/mon)					Weigh gain (gram/month)					Mean MUAC					Mean length-for-age z-score					Mean weight-for-length z-score					Mean weight-for-length z-score				
Maternal MUAC	< 21.0 cm																													
	=>21.0 cm																													
Maternal BMI	<18.5																													
	=>18.5																													
Birth weight	<2500 gm																													
	=> 2500 gm																													
Maternal age	<30 years																													
	=> 30 years																													
Gravidity	<3																													
	=>3																													
Gender	Male																													
	Female																													

References

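### Read literally, SAP Table 3 counts infant deaths and hospitalizations in a set that cannot contain an infant who died, has no row for maternal deaths, and conflicts with the protocol's safety denominator

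*SAP*

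**What the plan says.** **Analysis set.** SAP 12: "The primary analysis will be by intention-to-treat (ITT) perform for those who had anthropometry at 6 months". The SAP gives no other meaning of intention-to-treat and names no safety population.

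**Results table.** SAP 17, Table 3, is titled "Outcomes at 6 months in the Intention-to-treat analysis". Each arm has one N, left blank, above both the growth rows and the adverse-event rows. Adverse events are shown as number over total. The infant block lists infant deaths, hospitalization and injectable therapy. The maternal block lists the same three rows, infant deaths included.

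**Mortality definitions (SAP 10.4).**
- Infant: "Any infant death under one year of age".
- Neonatal, days 0-27 of life: "Numerator: # deaths <28 days Denominator: # live births".
- Maternal: "Maternal death from any cause related to or aggravated by pregnancy or its management (excluding accidental or incidental causes", limited to pregnancy, childbirth and the 42 days after.

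The same section makes death one of the criteria for an SAE.

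**Entry to the cohort.** SAP 7: "Infants with a live birth outcome, captured within 168 hours (0-6 days". Birth weight below 1500 g and severe illness are exclusions. Protocol 6.5 allows the family 24-48 hours to decide.

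**Protocol rule.** Protocol 10, Safety outcomes, reports the proportion with "at least one SAE during the follow-up period (from enrolment to 179th day", by category with death as one category. The denominator is all enrolled participants for women and all recorded newborns for infants. Protocol 8.1 asks for death from any circumstance to be reported.

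**The concern.** An infant who dies before the 6-month visit has no 6-month anthropometry. If Table 3 uses the set that its title names, the infant-death row is zero in every arm whatever happened. Hospitalizations among infants who died or were lost to follow-up drop out too. An analyst who follows the SAP alone gets a different safety table from one who follows the protocol, and the choice of denominator could then be made after the results are known.

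On the maternal side, the definition stops at day 42 and leaves out incidental causes, while the intervention and follow-up run to about day 179. The table shell has no row for a maternal death of any kind.

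The neonatal rate has a smaller problem. Infants must be alive, eligible and consented to enter, so deaths before enrolment are never in the numerator, and the trial cannot estimate a rate per live birth in the population sense.

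Mortality by arm matters to readers here: Protocol 1.1.2 itself cites studies in which azithromycin reduced all-cause under-five mortality.

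**Working it through.** **Step 1. Confirm that the 4% mortality allowance is the plan's working figure.** Inputs from Protocol 11: difference 0.12 cm/month, SD 0.5, one-sided alpha 0.025, power 80%, drop-out 14% (10% loss to follow-up plus 4% infant deaths). A t-based calculation gives power 0.7993 at 273 per arm and 0.8007 at 274, matching the stated 274 and 0.801. Inflation: 274 / (1 - 0.14) = 318.6, so 319 per arm and 957 in all. The plan's figures reproduce.

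**Step 2. Infants outside the 6-month-anthropometry set, at the planning rates.**
- Deaths per arm: 0.04 × 319 = 12.8. All arms: 0.04 × 957 = 38.3.
- Lost to follow-up per arm: 0.10 × 319 = 31.9.
- Total outside the set per arm: 0.14 × 319 = 44.7, leaving about 274.

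The death row is therefore 0 of about 274 per arm under the literal SAP reading, and about 13 of 319 per arm when all randomised infants are counted. The true mortality is unknown. Over an assumed range of 2% to 6%:

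| Assumed infant mortality | Deaths per arm | Deaths, all arms |
|---|---|---|
| 2% | 6.4 | 19 |
| 4% (plan) | 12.8 | 38 |
| 6% | 19.1 | 57 |

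**Step 3. Maternal follow-up outside the 42-day definition.** Days after day 42: 179 - 42 = 137. The share is 137 / (179 - enrolment day).
- Enrolled day 0: 137 / 179 = 76.5%.
- Enrolled day 6: 137 / 173 = 79.2%.

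This is a share of follow-up time in all three arms. The documents give no maternal death rate, so it cannot be turned into a number of deaths.

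**Step 4. Infant definition.** Follow-up ends at day 179, and every infant death up to then is a death before one year. Nothing is lost.

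**Step 5. Neonatal definition.** Deaths before enrolment (day 0-6) precede randomisation. They are missing from the population rate but cannot differ by assigned arm. The window also closes at day 27, before azithromycin is given at day 42, so this rate does not inform on that component.

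**Step 6. SAP against protocol.**

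| Item | Protocol 10 | SAP |
|---|---|---|
| Period for deaths | Enrolment to day 179 | Three different windows (10.4) |
| Denominator, women | All enrolled | Not stated; Table 3 title implies the 6-month set |
| Denominator, infants | All recorded newborns | Not stated; same implication |
| Maternal death reported | Yes, as an SAE category | No row in Table 3 |

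**The case against.** The strongest reply is that the exclusion comes only from joining two places in the SAP. The restricting sentence in SAP 12 is about the primary analysis, and what follows it concerns growth. Table 3 leaves N blank and shows adverse events as number over total, which permits a row-specific denominator. A row for infant deaths would be pointless if only measured infants counted, so the authors probably did not intend the literal reading. Protocol 10 already gives a usable rule, and the SAP does not revoke it. This stands as far as intent goes. It does not settle the matter: the SAP uses one term, defines it once, and puts the death row under it.

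A reader might go further and infer that a mortality difference would never come to light. The documents do not support that. Death is an SAE criterion in SAP 10.4. SAP 15 sends SAE differences to the DSMB, which considers estimates, confidence intervals and p-values for harm. Protocol 8.1 and 8.2 send fatal events to the DSMB and IRB within 72 hours.

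Three other inferences also fail:
- The one-year infant definition is longer than follow-up, but it discards no observed death.
- Missing pre-enrolment neonatal deaths limit comparison with population rates; they do not bias the comparison between arms.
- A restriction on infant anthropometry would not by itself remove a mother who died while her infant was measured. The missing row is what leaves her out of Table 3.

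The infant-death label in the maternal block looks like a copying error, but it still leaves maternal deaths without a place in the table.

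**Conclusion.** The concern holds as a defect of planned tabulation and a conflict between SAP and protocol. Read literally, SAP 12 and Table 3 together leave out every infant who died before the 6-month visit (about 13 per arm, 38 of 957, at the plan's 4%) and the hospitalizations of those lost to follow-up. The 42-day maternal definition leaves 76.5% to 79.2% of maternal follow-up uncovered, and Table 3 has no maternal-death row.

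It would be too strong to say that deaths are excluded by design, or that only deaths on treatment are affected. The first depends on reading the Table 3 title through SAP 12 with N left blank. On the second, the gap covers deaths during follow-up in all arms, control included.

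The figures assume that mortality and loss are as planned, that deaths occur before the 6-month visit, and that the anthropometry in SAP 12 means the infant's, since the primary outcome is infant length velocity. Collection and monitoring of deaths are not in question, and the primary growth analysis and sample size are unaffected by this point.

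**What to change.** In the SAP:
1. Define a safety set of all randomised mother-infant dyads, by assigned arm.
2. In 10.4, report all-cause infant deaths and, separately, all-cause maternal deaths from randomisation to day 179. If neonatal death is kept, define it as death from randomisation to day 27 per randomised infant.
3. In Table 3, use the number randomised in the arm as the denominator for every adverse-event row, say so in a footnote, and change the maternal infant-deaths row to maternal deaths.
4. Reconcile this wording with Protocol 10, stating that recorded newborns means all randomised infants.
5. Show the number with vital status known at day 179 in each arm, since deaths after loss to follow-up may not be known.

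The cost is SAP and table-shell wording, best settled before the allocation code is revealed. Adverse-event and verbal autopsy forms (Protocol 8.1, 8.2) and vital status at every visit (Protocol 7.3) already supply the data. Sample size does not change. The one small downside is that the rates will not be directly comparable with population mortality rates.

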10.5. Co-variates definition

Variable	Definition	Source
Preterm birth (PTB)	Live birth <37 completed weeks (and very preterm birth: live birth <32 completed weeks)	Baseline

Preterm delivery	Any birth outcome ≥ 22 and < 37 completed weeks based on LMP or Ultrasound data, whichever is available.	Baseline
Gravidity	Self-reported number of time woman got pregnant, including the enrolled child	Baseline
Parity	Number of live births (plus stillbirths)	Baseline
Prelacteal feeding (<72 hours)	Infant receives any liquids of foods other than breast milk, vitamins, minerals, or medicines identified at baseline (e.g., honey, ghee, boiled water, goat's milk, ritual fluids).	Baseline
Exclusive breastfeeding	Infant receives breast milk and nothing else except vitamins, minerals, or medicines (e.g., ORS, drops, or syrups). Breast milk can be breast or bottle fed and from mother or wet nurse.	Follow-ups
Predominant breastfeeding	Infant receives breast milk as the predominant source of nourishment. Infant may also receive other liquids (water, fruit-juice, water-based drinks, ritual fluids) or vitamins, minerals or medicines. Infant may NOT receive non-human milk or food-based fluids.	Follow-ups
Partial breastfeeding	Infant receives breast milk and infant formula or non-human milk (also may receive any other liquids).	Follow-ups
No breastfeeding	Infant receives no breast milk.	Follow-ups
Solid or semi-solid feeding	Infant receives solid, semi-solid, or soft foods.	Follow-ups
Age at introduction of solid foods	Age at which caregivers begin to provide solid, semi-solid, or soft foods.	Follow-ups
Early initiation of breastfeeding	Infant was breastfed within 1 hour of birth (includes infants who die beyond one hour of birth).	Baseline
Exclusive breastfeeding duration	Total time that infant was exclusively breastfed (in weeks) [could also assess breastfeeding duration past introduction of complementary food]	Follow-ups
Adherence to intervention	Mean percent of assigned supplement that was consumed (out of total eligible and supplementation time)	Follow-ups
Total time on supplement	Total time BEP supplement consumed during lactation (days)	Follow-ups
Kcals per day (from supplement)	Mean kcals consumed per day from supplement	Follow-ups
Protein per day (from supplement)	Mean protein (g) consumed per day from supplement	Follow-ups
Kcals per day (dietary intake)	Mean kcals consumed per day in maternal diet (not including BEP supplement)	Follow-ups
Carbohydrates per day (dietary intake)	Mean carbohydrate (g) consumed per day in maternal diet (not including BEP supplement)	Follow-ups

Protein per day (dietary intake)	Mean protein (g) consumed per day in maternal diet (not including BEP supplement)	Follow-ups
Fat per day (dietary intake)	Mean fat (g) consumed per day in maternal diet (not including BEP supplement)	Follow-ups
Mode of delivery	
 1. Vaginal 2. Assisted vaginal (forceps or vacuum) 3. Elective C-section 4. Emergency C-section 	Baseline
C-section indication	
 1. Obstructed/prolonged labor 2. Fetal presentation (e.g. breech) 3. Cord prolapse 4. Fetal intolerance of labor 5. Maternal hypertension/pre-eclampsia, eclampsia 6. Prior c-section (repeat) 7. Elective (planned) 8. Other _____ 	Baseline
Onset of labor	
 1. Spontaneous – contractions started on their own 2. Induced – intervention used to start contractions 3. None – c-section without start of labor 	Baseline
Rupture of membranes (ROM)	
 1. Spontaneous – membranes ruptured on their own 2. Artificial – intervention used to rupture membranes 	Baseline
PROM (premature rupture of membranes)	Spontaneous rupture of membranes before onset of labor	Baseline
PPROM (preterm premature rupture of membranes)	Spontaneous rupture of membranes before onset of labor at < 37 completed weeks	Baseline
Spontaneous preterm birth	Birth before 37 completed weeks (37 0/7 weeks) after spontaneous labor	Baseline
Labor augmentation	Anything done to help labor progress (e.g. oxytocin, artificial ROM)	Baseline
Obstructed labor (proxy)	Any maneuvers or instruments (e.g. forceps) were needed to help deliver the baby OR c-section due to obstructed/prolonged labor	Baseline

11. Procedure for data cleaning

Data is being collected on the tablets and sync live on server. The data analyst verifies or check through queries using Stata syntax on weekly basis and where required we asked repeat home visits until next due follow-up schedule. Forms are designed to reduce outliers by placing restricted ranges built in which shows errors if range exceed normal limits. Mostly variables are visualized by Box plot, histograms and scatter plot for distribution and detect errors.

12. Statistical plan and analysis goal

The primary analysis will be by intention-to-treat (ITT) perform for those who had anthropometry at 6 months. All analyses will be done using Stata software version 16. The WHO 2009 Child Growth Standards will be used for age-sex standardization of child length, weight, head circumferences, MUAC and weight-for-height. Descriptive analysis of each arm will be conducted, and percentages or continuous data with SD will be reported.

The baseline characteristics will be assessed by arm. Outcomes of mean length velocity, growth velocity, weight gain, z scores and change in z score from 0-6 month will be compared using one way analysis of variance (ANOVA). Tukey's test will be used for multiple comparisons. As determined *a priori* the analysis will be adjusted for the birth weight and length of infant, maternal MUAC at enrollment, maternal age, gravida, maternal body mass index and gender of child using general linear model (GLM). Mixed model analysis will be used to compare change in outcome per month in the intervention arm compared to the control arm. Using repeated measures ANOVA, the analysis will report beta coefficients and 95% CI. The coefficients represents the rate of change in outcome per month. For covariate adjustment, an unadjusted and stepwise adjusted model will be run. Trajectories will be plotted for mean length and weight by age for each arm, and monthly z scores were also be plotted.

13. Potential sub-group analysis

The following variables will be considered for sub-group analysis for primary and secondary outcomes:

1. Birth weight i.e. <2500 gm and => 2500 gm
2. Maternal MUAC at enrolment i.e. < 21.0 cm and =>21.0 cm
3. Maternal age i.e. <30 years and => 30 years
4. Gravidity i.e. <3 and =>3
5. Maternal BMI i.e. <18.5 kg/m² and =>18.5 kg/m²
6. Gender of child

14. Missing Data

We will treat missing data as it is, no imputation will be applied. We discussed that due to growth flattering during this age, imputation maybe unreliable.

15. Interim analysis

Data Safety and Monitoring Board of the trial will request an independent statistician to run interim analysis when 50% of the enrollment will complete the 6 months follow-ups in the trial. The analysis will be coded, and the findings will on difference in primary, secondary outcomes and Serious Adverse Events will be shared to DSMB in blinded coding. The DSMB will review results from the interim data analysis and will determine whether stopping boundaries have been crossed. Additional interim analyses may be completed and reviewed by the DSMB, per the advisement of the DSMB chair. The DSMB may, at its own discretion, ask the interim analysis to be done earlier or additional interim analyses to be completed on an ad hoc basis. Based on the trial safety monitoring and interim analysis, the following may be the key decision/s of DSMB pertaining to the trial:

- i. No action needed; trial continues as planned.
- ii. Early stopping due, for example, to clear benefit or harm of an intervention/s, uselessness, or external evidence.
- iii. Extending recruitment (based on actual control arm response rates being different to predicted rather than on emerging differences) or extending follow-up.
- iv. Stopping an arm of the multi-arm trial.
- v. Sanctioning and/or proposing protocol changes

While stopping rules will be utilized to help the DSMB to assess the justification of trial continuation, the DSMB will take into account the balance of risks and benefits as well as consistency with external evidence. Thus, the DSMB recommendation to continue or discontinue will not be based on any single issue or value in any of the analyses, but a comprehensive analysis considering multiple issues around the trial.

The DSMB may recommend termination or modification of the study if:

- i. In an interim analysis, there is strong evidence of a benefit (increases length velocity and/or secondary outcome) from the study intervention (O'Brien Fleming rule, $p < 0.05$).

- ii. In an interim analysis, there is strong evidence of harm (incidence of SAEs) from the study intervention. For harm assessment, no fixed statistical rules will be applied, but the DSMB will holistically consider point estimates and confidence intervals for SAE incidence differences, p-values from appropriate statistical tests and other relevant factors, when determining its recommendation about study continuation or discontinuation.

16. Background characteristics of participants

The background characteristics involved during screening, recruitment, or enrolment prior to taking any intervention will be considered baseline characteristics. Maternal and infant anthropometry at birth (baseline, within 0-6 days of birth) and then on monthly basis until 6 months of age. Every month, 24 hours food recall data will be collected from every enrolled LW participant. The number of times each participant will be contacted for outcome assessment is summarized in table 3. Moreover, frequencies and percentages will be used to summarize categorical data and mean and SD for continuous variables will be calculated.

17. Sample figures and tables

Figure 1 | Screening, Randomization, and Analysis

[figure not shown]

Table 2 | Baseline characteristics

Characteristics	Standard of care and only exclusive breastfeeding counselling (N=319)	BEP with standard of care and exclusive breastfeeding counselling (N=319)	BEP plus single dose of azithromycin to infant with standard of care and exclusive breastfeeding (N=319)
Maternal characteristics			
Age – Mean (years)			
Nutrition status - Mean			
Weight (kg)			
Body mass index (kg/m2)			
Mid-upper-arm-circumference (cm)			
Education – no./total no. (%)			
No formal education			
Primary			
Secondary			
Intermediate			
Undergraduate or above			
Obstetric history - Mean			
Gravidity			
Parity			
Initiation of breastfeeding soon after birth – no./total no. (%)			
Colostrum given			
Breastfeeding started within one hour of birth			
Prelacteal feeding given			
Household characteristics - Mean			
Household density**			
Material used for the floor of the house – no./total no. (%)			
Cement			
Natural/mud			
Wood			
Tiles			
Material used for the wall of the house – no./total no. (%)			
Cement			
Natural/mud			
Wood			
Tiles			
Temporary sheet			
Source of drinking water – no./total no. (%)			
Piped			
Community tap water			
Water tanker			
Bottle			
Boring			
Filtered Water			
Infant characteristics			

Demographic characteristics – no./total no. (%)

Age (Hours)

Gender

Male

Female

Anthropometric measures – Mean

Length (cm)

Weight (kg)

Mid-upper-arm-circumference (cm)

Head circumference (cm)

Length-for-age z-score

Weight-for-age z-score

Weight-for-length z-score

Nutritional status – no./total no. (%)

Wasting§

Stunting¶

Underweight||

* Plus-minus values are means \pm SD.

** Calculated as number of people per room at household.

§ Stunting was defined as a height-for-age z score lower than -2 SD.

¶ Wasting was defined as a weight-for-height z score lower than -2 SD.

[figure not shown]
|| Underweight was defined as a weight-for-age z score lower than -2 SD.

Table 3 | Outcomes at 6 months in the Intention-to-treat analysis*

[figure not shown]
Outcomes	Standard of care and only exclusive breastfeeding counselling	BEP with standard of care and exclusive breastfeeding counselling	BEP plus single dose of azithromycin to infant with standard of care and exclusive breastfeeding	Pairwise comparison $\Delta \pm SD$	p-value
	N=	N=	N=		
Primary outcomes - Mean					
Length velocity of infant (cm/mon)					
Secondary outcomes					
Infant related					
Growth – Mean					
Growth velocity (gm/kg/day)					
Mid-upper-arm-circumference (cm)					
Head circumference (cm)					
Length-for-age z-score					
Weight-for-age z-score					
Weight-for-length z-score					
Head circumference-for-age z-score					
Nutritional status - no./total no. (%)					
Wasting					
Stunting					
Underweight					
Adverse event - no./total no. (%)					
Infant deaths					
Hospitalization					
Injectable therapy					
Maternal related					
Nutritional status - Mean					
Maternal weight gain (kg)					
Mid-upper-arm-circumference (cm)					
Body mass index (kg/m ²)					
Adverse event - no./total no. (%)					
Infant deaths					
Hospitalization					
Injectable therapy					

* Plus–minus values are means \pm SD.

Figure 2 | Monthly trends for z-scores
2a | Monthly mean length-for-age z-scores

2b | Monthly mean weight-for-age z-scores

2c | Monthly mean weight-for-length z-scores

[figure not shown]

Table 4 | Subgroup analysis

Indicator	1	2	3	Δ	P-value	1	2	3	Δ	P-value	1	2	3	Δ	P-value	1	2	3	Δ	P-value	1	2	3	Δ	P-value					
Subgroups	Mean length velocity (cm/mon)					Weigh gain (gram/month)					Mean MUAC					Mean length-for-age z-score					Mean weight-for-length z-score					Mean weight-for-length z-score				
Maternal MUAC	< 21.0 cm																													
	=>21.0 cm																													
Maternal BMI	<18.5																													
	=>18.5																													
Birth weight	<2500 gm																													
	=> 2500 gm																													
Maternal age	<30 years																													
	=> 30 years																													
Gravidity	<3																													
	=>3																													
Gender	Male																													
	Female																													

References

